## 7. RATIONALE FOR TREATMENT REGIMENS

PrEP strategies that have been evaluated for efficacy have used the nucleos(t)ide reverse transcriptase inhibitor (NRTI) TDF alone or in combination with FTC, including a co-formulation of TDF/FTC in a once-daily pill (19). Agents active at the pre-integration stage of viral replication that may prevent the establishment of HIV-infected cells are thought to be more suitable than post-integration drugs like protease inhibitors (PI), although data to support this supposition are limited (20). In contrast to NRTIs, non-nucleoside reverse transcriptase inhibitors (NNRTIs) and PIs generally achieve lower drug concentrations in the genital tracts of males and females as compared to blood plasma; a potential liability when attempting to reduce genital tissue susceptibility to infection (21). The availability of new drugs such as those that block viral DNA integration or entry through CCR5 are mechanistically attractive; however, comparative trials of different agents for PrEP have yet to be performed, and the optimal correlates of protection in all populations have yet to be defined (22). To date, only TDF/FTC with daily dosing has been FDA approved for HIV prevention among at-risk populations in the US.

A comprehensive understanding of the pharmacology of antiretroviral drugs in genital secretions and tissues is essential to define the most appropriate drug candidates and dosing strategies for PrEP. Correlating drug levels, drug dosing (including route and dose amount), and viral protection are critical parameters that are still being defined. Early findings from animal studies suggested that the high level of protection by pre-exposure dosing strategies may be related to the long persistence of TFV-DP and emtricitabine triphosphate (FTC-TP) in mononuclear cells. Rapid FTC distribution in tissues and long intracellular TFV persistence complement each other to maximize PrEP efficacy (23). The intracellular assay used in the iPrEx study was sensitive enough to detect drug for approximately 14 days after the last dose taken, based on TFV-DP half-life extrapolation, assuming the half-lives of 39 hours and 150 hours for FTC-TP and TFV-DP, respectively (24). Detectable (at the 10 ng/mL level) plasma concentrations of FTC and TFV, with half-lives of 10 to 14 hours, would be expected to last for approximately 2-3 days after dosing (25).

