The Partners-PrEP study (a population of heterosexual serodiscordant men and women in Kenya and Uganda) also found that drug levels strongly predicted TDF/FTC and TDF efficacy - detectable drug (using a more sensitive assay than the primary iPrEx data) predicted 86% efficacy for TDF alone, and 90% efficacy for TDF/FTC (contrast 67% and 75%, in the overall population, respectively). The Partners-PrEP study found three distinct patterns of adherence: 1. Seventy percent of participants had sustained TFV drug levels >40 ng/mL; 2. Ten percent of the population had levels that were detectable most of the time (10-40 ng/mL), but dipped occasionally to undetectable levels; and 3) Twenty percent of the population had persistently undetectable drug levels (52). It is probable that prospective, real-time identification of these non-adherent populations (although it remains unclear what percentage this would represent in iPrEx [the MSM population studied to date] – one would suspect the overwhelming majority) and applying intensive adherence interventions would be critical to the success of a PrEP effort.

In this study we will use intracellular TFV-DP from DBS as our primary outcome measure of adherence. Anderson and Castillo-Mancilla have developed technology using LC-MS/MS to measure intra-erythrocytic TFV-DP levels, which provide a measure of average tenofovir exposure (adherence) over the preceding 30-90 days, not unlike a Hemoglobin A1C measurement (53). Such measurements can be made from DBS samples, which are stable over time and easy to handle. The key characteristic that enables TFV-DP to be used as an adherence biomarker is the 17-day half-life of TFV-DP in red blood cells. A similar long-term objective measure of adherence, tightly correlated with virologic suppression has been validated using scalp hair samples (54). However, sampling of scalp hair has proven variably acceptable among diverse populations (unpublished data, ACTG A5257).

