#### Hypothesis II

Intracellular TFV-DP concentrations levels will correlate with self-reported adherence by daily texting through iTAB,

For the primary analysis, we will measure adherence using a drug level cutoff consistent with 6 or more doses per week, as measured by TFV-DP level > 1050 fmol/punch at weeks 4, 12, 24, 36 and 48. This will be in the as-treated group who are on-PrEP (censoring those on permanent or temporary discontinuation). A descriptive analysis of the proportion of women achieving adequate adherence by week of study will be conducted. Baseline versus 48 weeks proportion of adherence will be compared via Fisher's exact test.

**In order to examine drug adherence surrounding the implementation of intensified interventions specific to women receiving targeted iNSC and those receiving PrEP-STEPS we will compare the change in levels pre- and post-intervention.**

Additional sensitivity analyses will be performed using alternative cutoffs of adherence. Intracellular FTC-TP levels will be compared to TFV-DP for discrepancy of recent dosing that would be reflective of the short half-life of FTC (past day) versus the past week of dosing that is informed by the long half-life of TDF.

Subgroup analysis will compare adherence and other outcomes between risk categories of women (e.g. serodiscordant partnerships with and without conception intentions, partner of elevated HIV risk, sex worker, recent STI, injection drug use, PEP users).

Adherence will be measured by self-report using daily text messaging through iTAB. We will validate iTAB reported adherence in women using the TFV-DP levels for correlation with the proportion of positive responses in the 34 days prior to the drug level (i.e. two half lives of TDF) in week 12, 24, 36 or 48 using the Spearman correlation coefficient.

The average days of adherence per week during this time will be calculated as number of days reporting doses taken in past 35 days divided by 35 multiplied by 7 and rounded to the nearest whole number. For each number of days per week of adherence (i.e. 0, 1, 2,3, 4,

5,6 and 7) the TFV-DP will be reported from mean (95% confidence interval) and median (IQR).

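### The FTC-TP versus TFV-DP comparison treats dried-blood-spot TFV-DP as a one-week measure, against the protocol's own 17-day half-life and 30-90 day window

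*Combined protocol and SAP*

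**What the plan says.** Among the sensitivity analyses in section 30.2 (under Hypothesis II), the plan compares intracellular FTC-TP with TFV-DP. A discrepancy is to be "reflective of the short half-life of FTC (past day"), set against TFV-DP, described as "versus the past week of dosing that is informed by the long half-life of TDF".

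Three other places bear on that window:

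- Section 10 states that dried blood spot (DBS) TFV-DP gives "average tenofovir exposure (adherence) over the preceding 30-90 days", and says that what makes it usable as an adherence marker is "the 17-day half-life of TFV-DP in red blood cells".
- Section 30.2, a few lines further on, correlates TFV-DP with the share of positive iTAB replies "in the 34 days prior to the drug level (i.e. two half lives of TDF").
- Section 7 cites a much shorter TFV-DP half-life for the intracellular assay of the iPrEx study, "assuming the half-lives of 39 hours and 150 hours for FTC-TP and TFV-DP, respectively".

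Section 10 is explicit about the matrix: "In this study we will use intracellular TFV-DP from DBS as our primary outcome measure of adherence". The schedule of evaluations (section 20) lists DBS for red-cell TFV-DP. It has no mononuclear-cell collection and no FTC-TP row.

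**The concern.** Section 30.2 gives one analyte two incompatible look-back windows, one week and 34 days, and justifies both by its half-life. Only the second agrees with section 10.

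The comparison is meant to separate recent dosing from longer-run dosing. That contrast depends on knowing what period each marker covers. If TFV-DP is taken to cover one week, a high value suggests doses in that week and a low value suggests few or none. With a 17-day half-life neither inference is safe, because most of the signal was laid down before the week began. Statements in the report about when women were or were not dosing could then be wrong. This matters in a study whose primary analysis is restricted to women who are on PrEP.

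**Working it through.** **Inputs from the documents**

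- Half-life of red-cell TFV-DP: 17 days (section 10).
- iTAB look-back: 34 days, stated to be two half-lives (section 30.2).
- Intracellular half-lives cited for the iPrEx assay: TFV-DP 150 hours = 6.25 days, FTC-TP 39 hours (section 7).
- Threshold for optimal adherence: 1050 fmol/punch (section 16.5.1).
- Reference level: mean 1352 fmol/punch, equated with 6 of 7 doses a week (section 16.5.2, a preliminary week-12 result in another study).

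**Assumptions.** First-order decay, constant dosing, and level proportional to dose frequency. The last puts daily dosing at 1352 × 7/6 = 1577 fmol/punch.

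**1. The plan's own figure.** 2 × 17 = 34 days. The iTAB look-back reproduces exactly, so section 30.2 is already using the 17-day half-life.

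**2. Share of the steady-state level from the last d days.** Share = 1 − 2^(−d/half-life).

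| Half-life | d = 7 | d = 30 | d = 34 | d = 90 |
|---|---|---|---|---|
| 17 days | 24.8% | 70.6% | 75.0% | 97.5% |
| 6.25 days | 54.0% | 96.4% | 97.7% | 100.0% |

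Varying the half-life from 14 to 20 days (an assumed range) moves the 7-day share only from 29.3% to 21.5%. For one week to supply 90% of the signal, the half-life would have to be 7 × ln 2 / ln 10 = 2.1 days.

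**3. Error in one direction: recent dosing, low level.** Starting from zero and taking all seven doses in the past week gives 1577 × 0.248 = about 392 fmol/punch. Read as a past-week measure, this looks like poor dosing.

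**4. Error in the other direction: no recent dosing, substantial level.** After 7 days without doses the level is multiplied by 2^(−7/17) = 0.752.

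- From 1577: about 1186, above 1050.
- From 1352: about 1016, just below 1050.

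Time to fall to 1050 is 17 × log2(start/1050): 10.0 days from 1577 and 6.2 days from 1352.

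**5. Accumulation at week 4.** Share of plateau after 28 days = 1 − 2^(−28/17) = 68.1%. A woman taking 6 of 7 doses throughout would measure about 0.681 × 1352 = 920. Daily dosing would give about 0.681 × 1577 = 1074.

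**6. The FTC-TP label.** At 39 hours, the last 24 hours supply 1 − 2^(−24/39) = 35% of the level, so the one-day label is also loose.

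**The case against.** The strongest reply is that the week is only explanatory wording. The plan says the two levels will be compared; the window enters no formula, cutoff or classification. Where a look-back does enter a calculation, in the iTAB analyses, the plan uses 34 or 35 days. Section 30 calls itself a brief description and defers to a formal SAP.

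Much of this stands. A reader might infer that women who stopped more than a week before the visit will be reported as recent users. The documents do not support that: no rule for discordant results is written, and high TFV-DP with low FTC-TP would be discrepant under either label. The worked example is also sensitive to its starting level. From 1352, seven days off already falls below 1050. If instead 1050 is taken as 6 of 7 doses, daily dosing is 1225 and seven days off leaves about 921. Even from 1577, the women who have been off drug for over a week yet remain above 1050 are those who stopped roughly 7 to 10 days earlier. The 1352 figure itself comes from men who have sex with men and transgender women.

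A second rescue is that the week fits mononuclear-cell kinetics. But the trial measures red-cell TFV-DP, and even at 150 hours one week supplies only 54%. Nor can the phrase be read as doses per week: it is paired with a one-day window and tied to half-life. The documents do not say where the one-week figure came from.

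What the reply does not remove is the contradiction. The stated window is wrong by the protocol's own figures, and the 24.8% share does not depend on any starting level.

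**Conclusion.** The concern holds as an internal inconsistency with a practical consequence for interpretation. By the protocol's 17-day half-life, about three quarters of a steady-state DBS TFV-DP level predates the week that section 30.2 assigns to it, given first-order decay and constant dosing. Conclusions about timing drawn on the one-week reading can be wrong in either direction. The fmol/punch examples illustrate this and also rest on the assumed proportional scaling.

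The reach is limited. This is a secondary comparison listed with the sensitivity analyses. A reader might take it to undermine the adherence endpoint, but the primary proportion above 1050 fmol/punch, the trigger for adherence support and the iTAB correlation do not use the one-week window. Severity is low; the correction is worthwhile because it is almost free.

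**What to change.** In section 30.2, and in the formal SAP due before database lock, replace the one-week description of TFV-DP with cumulative exposure over about 34 days. This is two half-lives, supplies 75% of the steady-state level, and matches the iTAB look-back. State that discordance will be read as recent (FTC-TP) versus cumulative (TFV-DP) dosing, and soften the one-day label for FTC-TP.

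Add one caution: low TFV-DP with high FTC-TP should not be labelled sustained poor adherence at week 4 or after a restart, because the level is then still accumulating. A consistent user at 6 of 7 doses would measure only about 920 at week 4 under the assumptions above.

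The cost is a sentence or two, with no change to the primary analysis. Separately, confirm that FTC-TP will be assayed and at which visits, since the schedule of evaluations names only TFV-DP. If it will not be, the comparison cannot be run as written.

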### **Secondary Objectives:**

To describe the characteristics of women seeking PrEP, a descriptive analysis will be performed for the following secondary endpoints:

- PrEP awareness and acceptability prior to study enrollment
- Perceived barriers and facilitators to PrEP use
- HIV knowledge pre- and post-study

Implementation secondary outcomes will include:

- Acceptability and feasibility of an HIV prevention program with a multimodal, intensive adherence package for PrEP delivery defined on a Likert scale
- Retention in an HIV prevention program that includes PrEP defined by making study visit
- Safety and tolerability of daily TDF/FTC given for PrEP including discontinuation for any adverse event, serious adverse events and adverse events (grade 2 or higher)
- HIV incidence in the observed cohort of PrEP users
- Frequency of clinically significant resistance among seroconverters

Additional sensitivity regression modeling will be performed for the factors associated with loss to follow up and discontinuation of TDF/FTC. Factors will included change in perceived and actual risk of HIV acquisition, fear of disclosure, demographics, socioeconomic status, social characteristics (e.g., medical mistrust, non-English language, cultural factors), co-occurring health problems or issues (e.g., untreated mental illness, ongoing substance use, violence, trauma), and low health/HIV and system literacy.

Risk compensation during study will be assessed by changes in the incidence of STIs (chlamydia, gonorrhea, HSV-2 and syphilis) during study and self reported sexual risk behavior over time by number of sexual partners (by HIV status) and number condomless sex acts.

All descriptive results will be reported as point estimates (mean or odds ratios as appropriate) and interval estimates (95% confidence intervals, interquartile ranges). All tests of significance for the secondary outcomes will be 2-sided and no adjustments will be made for multiple comparisons. A p-value of 0.05 will be considered statistically significant. Statistical analysis will be conducted using the statistical software R 3.1.1 ([www.r-project.org](http://www.r-project.org)).

## **31. INFORMED CONSENT**

The study will be overseen by the Institutional Review Boards of UCLA, UCSD, and participating clinical sites, and the study and all related study documents will be approved by all IRBs.

Although PrEP is recommended by the CDC and TDF/FTC has received FDA approval for a preventive/prophylactic indication, it is important that participants accessing resources understand the limitations of knowledge regarding PrEP, including effectiveness estimates, with precise efficacy dependent on, and likely proportional to daily adherence rates.

All participants will be required to sign a one-time consent for documenting understanding of study procedures, risks to self and intimate contacts, course of treatment including a behavioral risk-reduction component and adherence counseling activities, all as described in the informed consent and protocol.

**32. EXPERTS IN HIV CLINICAL CARE**

Numerous references are made to conditions for invoking opinion or consultation with experts in HIV clinical care, including:

- Incidental finding of HIV-positivity on rapid screening on initial intake
- Signs or symptoms consistent with PHI (Section 22.3, Table 1)
- Toxicity or intolerance to TDF/FTC requiring discontinuation
- Unclear attribution of toxicity to TDF/FTC and/or appropriate work-up

The HIV Clinical Care Expert will be considered the site PI, or if unavailable the protocol chair or his designee.

**33. HUMAN PARTICIPANTS**

**33.1. Institutional Review Board (IRB) Review and Informed Consent**

This protocol and the informed consent document and any subsequent modifications will be reviewed and approved by the IRB or ethics committee responsible for the oversight of the study. A signed consent form will be obtained from the participant. The consent form will describe the purpose of the study, the procedures to be followed and the risks and benefits of participation. A copy of the consent form will be given to the participant.

**33.2. Participant Confidentiality**

All laboratory specimens, evaluation forms, reports, and other records that leave the site will be stripped of any patient identifiers (name, birthdate, medical record number) and only identified by the coded PID in order to maintain participant confidentiality. All records will be kept locked. All computer entry and networking programs will be done with coded numbers only and analyzed centrally without any possibility of linking participant identity with participant data. Clinical information will not be released without written permission of the participant, except as necessary for monitoring by IRB and governmental agencies.

**34. PUBLICATIONS AND FINDINGS**

Publication of the results of this trial will be governed by LAC-PATH/CCTG policies. Any presentation, abstract or manuscript will be made available for review by pharmaceutical supporters prior to submission.

**35. BIOHAZARD CONTAINMENT**

As the transmission of HIV and other blood-borne pathogens can occur through contact with contaminated needles, blood and blood products; appropriate blood and secretion precautions will be employed by all personnel in the drawing of blood and shipping

and handling of all specimens for this study, as currently recommended by the Centers for Disease Control and Prevention and the National Institutes of Health.

All infectious specimens will be transported using packaging mandated in the Federal Code of Regulations, CDC 42 CFR Part 72. Please also refer to individual carrier guidelines, e.g., FedEx, Airborne, for specific instructions.

### **36. FUNDING**

California HIV Research Program  
Drug Supply from:  
Gilead Sciences  
Foster City, California

